9.2.2. Analysis of Secondary Endpoints

The proportion of subjects with an HbA1c <7.0% (53 mmol/mol) at Week 26 will be analyzed using a logistic regression model with terms for country (categorical) (applicable only for the analyses of the overall study population), treatment (categorical), baseline HbA1c (continuous), AHA status at study entry, and baseline eGFR (continuous). Summary measures from the analysis will include the odds ratio, 95% confidence interval for the odds ratio, and p-value for the comparison of treatment groups.

The secondary endpoints of fasting plasma glucose, body weight, systolic blood pressure and diastolic blood pressure will be analyzed separately by fitting constrained longitudinal data analysis models similar to that used for the primary endpoint. Sitting blood pressure collected in triplicate will be used for assessment of blood pressure as a secondary endpoint.

For the overall study population, the secondary efficacy endpoints of FPG, proportion of subjects with an HbA1c <7.0%, body weight, systolic blood pressure and diastolic blood pressure will be tested for each ertugliflozin dose versus placebo using a multiple testing procedure that strongly controls the overall Type I error rate at 0.05. For the China subpopulation, due to smaller sample size, which limits power for other secondary endpoints, only FPG and body weight endpoints will be tested for each ertugliflozin dose versus placebo using a multiple testing procedure that strongly controls the Type I error rate at 0.05. Therefore, a step-down hierarchical, sequential testing approach will be used, as follows:

Order (for Overall Study population)	Order (for China subpopulation)*	Endpoint (Change from Baseline to Week 26**)	Arm Comparison
1	1	HbA1c	15 mg ertugliflozin arm to placebo
2	2	HbA1c	5 mg ertugliflozin arm to placebo
3	3	FPG	15 mg ertugliflozin arm to placebo
4	4	FPG	5 mg ertugliflozin arm to placebo
5	5	Body Weight	15 mg ertugliflozin arm to placebo
6	6	Body Weight	5 mg ertugliflozin arm to placebo
7	N/A	HbA1c <7.0% at Wk 26	15 mg ertugliflozin arm to placebo
8	N/A	HbA1c <7.0% at Wk 26	5 mg ertugliflozin arm to placebo
9	N/A	Systolic BP	15 mg ertugliflozin arm to placebo
10	N/A	Systolic BP	5 mg ertugliflozin arm to placebo
11	N/A	Diastolic BP	15 mg ertugliflozin arm to placebo
12	N/A	Diastolic BP	5 mg ertugliflozin arm to placebo

* Hierarchical hypothesis testing for the China study population will only be performed for the HbA1c, FPG and body weight endpoints.

**Except for HbA1c <7.0% at Wk 26 endpoint.

Within each study population, starting with the first hypothesis, the test will be conducted at a 5% level of significance. If the hypothesis test is significant, then the next hypothesis within that study population will be tested at a 5% level of significance. Otherwise, testing ceases within this hierarchy within each study population. The testing sequence as specified above will be applied for the overall study population and the China subpopulation. The non-numbered items listed above will be assessed with 95% CIs and nominal p-values.

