The purpose of this trial is to evaluate the efficacy and safety of the addition of ertugliflozin to the treatment regimen of Asian subjects with T2DM who have inadequate glycemic control on metformin monotherapy. The results of this study are intended to support the registration of ertugliflozin in China.

Objectives and Hypotheses:

The objectives listed below will be assessed in the overall study population and also in the China subpopulation (ie, subjects enrolled from China) in parallel. All hypotheses will be tested in the overall population; the primary hypotheses and secondary hypotheses 1-4 will also be tested in the China subpopulation (see Statistical Section 9.2.1 and 9.2.2).

In subjects with T2DM and inadequate glycemic control on metformin monotherapy, the following are primary objectives and hypotheses of the trial, after 26 weeks:

1. **Objective:** To assess the effect on HbA1c of 15 mg ertugliflozin relative to placebo.
Hypothesis: The mean reduction from baseline in HbA1c for 15 mg ertugliflozin is greater than that for placebo.
2. **Objective:** To assess the effect on HbA1c of 5 mg ertugliflozin relative to placebo.
Hypothesis: The mean reduction from baseline in HbA1c for 5 mg ertugliflozin is greater than that for placebo.
3. **Objective:** To assess the safety and tolerability of ertugliflozin.

The secondary objectives and hypotheses of the trial are, after 26 weeks:

1. **Objective:** To assess the effect on fasting plasma glucose (FPG) of 15 mg ertugliflozin relative to placebo.
Hypothesis: The mean reduction from baseline in FPG for 15 mg ertugliflozin is greater than that for placebo.

2. **Objective:** To assess the effect on FPG of 5 mg ertugliflozin relative to placebo.

Hypothesis: The mean reduction from baseline in FPG for 5 mg ertugliflozin is greater than that for placebo.

3. **Objective:** To assess the effect on body weight of 15 mg ertugliflozin relative to placebo.

Hypothesis: Ertugliflozin 15 mg reduces body weight relative to placebo.

4. **Objective:** To assess the effect on body weight of 5 mg ertugliflozin relative to placebo.

Hypothesis: Ertugliflozin 5 mg reduces body weight relative to placebo.

5. **Objective:** To assess the proportion of subjects with an HbA1c <7.0% (53 mmol/mol) treated with 15 mg ertugliflozin relative to placebo.

Hypothesis: The proportion of subjects with an HbA1c <7.0% (53 mmol/mol) treated with 15 mg ertugliflozin is greater than that for placebo.

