2. STUDY OBJECTIVES, HYPOTHESES AND ENDPOINTS

2.1. Objectives and Hypotheses

The objectives listed below will be assessed in the overall study population and also in the China subpopulation (subjects enrolled from China) in parallel. All hypotheses will be tested in the overall population; the primary hypotheses and secondary hypotheses 1-4 will also be tested in the China subpopulation (see Statistical Sections 9.2.1 and 9.2.2).

In subjects with T2DM and inadequate glycemic control on metformin monotherapy, the following are primary objectives and hypotheses of the trial, after 26 weeks:

1. **Objective:** To assess the effect on HbA1c of 15 mg ertugliflozin relative to placebo.
Hypothesis: The mean reduction from baseline in HbA1c for 15 mg ertugliflozin is greater than that for placebo.
2. **Objective:** To assess the effect on HbA1c of 5 mg ertugliflozin relative to placebo.
Hypothesis: The mean reduction from baseline in HbA1c for 5 mg ertugliflozin is greater than that for placebo.
3. **Objective:** To assess the safety and tolerability of ertugliflozin.

The secondary objectives and hypotheses of the trial are, after 26 weeks:

1. **Objective:** To assess the effect on fasting plasma glucose (FPG) of 15 mg ertugliflozin relative to placebo.
Hypothesis: The mean reduction from baseline in FPG for 15 mg ertugliflozin is greater than that for placebo.
2. **Objective:** To assess the effect on FPG of 5 mg ertugliflozin relative to placebo.
Hypothesis: The mean reduction from baseline in FPG for 5 mg ertugliflozin is greater than that for placebo.
3. **Objective:** To assess the effect on body weight of 15 mg ertugliflozin relative to placebo.
Hypothesis: Ertugliflozin 15 mg reduces body weight relative to placebo.
4. **Objective:** To assess the effect on body weight of 5 mg ertugliflozin relative to placebo.
Hypothesis: Ertugliflozin 5 mg reduces body weight relative to placebo.
5. **Objective:** To assess the proportion of subjects with an HbA1c <7.0% (53 mmol/mol) treated with 15 mg ertugliflozin relative to placebo.

Hypothesis: The proportion of subjects with an HbA1c <7.0% (53 mmol/mol) treated with 15 mg ertugliflozin is greater than that for placebo.

6. **Objective:** To assess the proportion of subjects with an HbA1c <7.0% (53 mmol/mol) treated with 5 mg ertugliflozin relative to placebo.

Hypothesis: The proportion of subjects with an HbA1c <7.0% (53 mmol/mol) treated with 5 mg ertugliflozin is greater than that for placebo.

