9.1. Sample Size Determination

The sample size determination is based on the primary endpoint, reduction in HbA1c from Baseline to Week 26, within the subjects enrolled from China. Assuming a standard deviation (SD) of 1.0%,¹¹⁻¹⁸ a sample size of 105 subjects from China per group (total of 315 subjects from China) provides approximately 95% power to detect a difference in HbA1c of 0.5% between each ertugliflozin dose and placebo (and approximately 90% power for detecting this difference for both doses vs. placebo) using a two-sided 0.05 alpha level test. To control the overall Type I error rate at 0.05 within each population (overall study

population and the China subpopulation) a sequential testing approach will be used across the primary and secondary efficacy endpoints for which hypotheses will be tested, and for the two doses of ertugliflozin. Assuming a drop-out rate of 20% at Week 26 [(ie, either subjects who discontinue from the study, discontinue administration of IP (Investigational Product) or subjects who take rescue medication and are censored], approximately 396 subjects from China (132 per group) will be randomized. Additionally, this study will have approximately 99 subjects from at least two other Asian countries.

The total sample size for this study is approximately 495 randomized subjects.

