The two primary hypotheses, comparisons of each ertugliflozin dose to placebo will be tested sequentially to control the overall Type I error rate at 0.05 within each population (the overall study population, and China subpopulation) (see below for sequence of testing for the overall population and the China subpopulation). Within each of these two populations, the 15 mg dose will be tested first, and the 5 mg dose will be tested if and only if a statistically significant result is achieved for 15 mg.

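### Limited power is a reason to put HbA1c <7.0% and blood pressure last in the China testing sequence, not to leave them out (cheap improvement, minor weight)

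*Combined protocol and SAP*

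**What the plan says.** Error is controlled separately in the overall and China populations. Section 9.2.1 has the primary hypotheses "tested sequentially to control the overall Type I error rate at 0.05 within each population". Section 9.2.2 sets out a step-down table. In each population, "starting with the first hypothesis, the test will be conducted at a 5% level of significance", and then "If the hypothesis test is significant, then the next hypothesis within that study population will be tested at a 5% level of significance". At the first non-significant result, testing in that population ends.

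The overall sequence has 12 steps: HbA1c, FPG, body weight, HbA1c <7.0%, systolic BP and diastolic BP, each at 15 mg and then 5 mg. The China sequence has only the first six, and its last six rows are marked not applicable. The reason given is that, "due to smaller sample size, which limits power for other secondary endpoints, only FPG and body weight endpoints will be tested". The table footnote repeats the limit: "Hierarchical hypothesis testing for the China study population will only be performed for the HbA1c, FPG and body weight endpoints". Endpoints without an order number get 95% confidence intervals and nominal p-values. Section 2.1 agrees: "the primary hypotheses and secondary hypotheses 1-4 will also be tested in the China subpopulation". The protocol summary carries the same limit, both in its objectives and in its statistical methods. No error-rate reason for the shorter China sequence appears anywhere.

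**The concern.** The reason given does not lead to the choice made. In a fixed sequence, a test at order 7 or later is carried out only after orders 1-6 have all succeeded, so it takes nothing from them. An endpoint with modest power belongs late in such a sequence. Removing it gives up the chance of a controlled claim without protecting any other test.

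China is also the population of most interest. The summary states: "The results of this study are intended to support the registration of ertugliflozin in China". The sample size in Section 9.1 is built on the Chinese subjects. As written, the trial can make no type-I-error-controlled China statement on HbA1c <7.0% or blood pressure, whatever the data show, although the overall population tests the same hypotheses.

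**Working it through.** **Inputs from the documents.** Section 9.1: 105 evaluable Chinese subjects per arm, difference 0.5%, SD 1.0%, test made "using a two-sided 0.05 alpha level test", 20% drop-out, 396 Chinese subjects among about 495 randomized. Section 1.3: Phase 2 systolic effects of -2.77 to -3.69 mmHg and diastolic effects of -2.03 to -4.12 mmHg.

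**Assumed, because the plan does not give them.** Placebo Week 26 HbA1c mean 7.4-8.0% (SD 1.0%); SD 10-14 mmHg for systolic and 7-9 mmHg for diastolic BP; correlation 0.3 between endpoints; FPG and body weight power equal to that of HbA1c. The correlation of 0.5 between doses follows from the shared placebo arm with equal allocation.

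**The plan's own figures.**
- Expected z = 0.5 / (1.0 × √(2/105)) = 3.62. Power = Φ(3.62 − 1.96) = 0.952 (0.950 with the noncentral t).
- Both doses: 0.952² = 0.906 if independent, 0.915 with correlation 0.5.
- 105 / 0.8 = 131.25, so 132 per arm and 396 in China.

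The stated 95%, 90% and 396 are reproduced.

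**Error control.** Let the first true null sit at position k. A false rejection anywhere requires that null to be rejected at 5%, so the family-wise error is at most 0.05 whatever the length of the sequence. A simulation of the 12-step China sequence gave 0.049-0.051 for every k. When the first six effects are real and a later null is true, the six-step sequence gives 0 and the 12-step sequence about 0.05.

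**How limited is China power?** China is 396/495 = 80% of the trial, so its standard errors are √(495/396) = 1.12 times the overall ones. The overall comparison below uses 165 × 0.8 = 132 evaluable per arm.
- HbA1c <7.0%, placebo mean 7.8%: responders Φ(−0.8) = 0.212 against Φ(−0.3) = 0.382. With the pooled proportion 0.297, the null SE is √(0.297 × 0.703 × 2/105) = 0.063, and the alternative SE is 0.062. Power = Φ((0.170 − 1.96 × 0.063)/0.062) ≈ 0.77. Over placebo means 7.4-8.0% it is 0.73-0.82 (overall 0.82-0.90). A simulated baseline-adjusted logistic test, with other assumed inputs, gave 0.62-0.86.
- Systolic BP, 2.77 mmHg, SD 12: SE = 12 × √(2/105) = 1.66, power Φ(1.67 − 1.96) = 0.39 (overall 0.47). Range over the assumed inputs: 0.30-0.76.
- Diastolic BP, 2.40 mmHg, SD 8: SE = 1.10, power Φ(2.17 − 1.96) = 0.58 (overall 0.68). Range: 0.37-0.99.

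China power is lower than overall power, but only by about 0-10 percentage points.

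**Cumulative chance of a confirmatory China claim.** One scenario, with the inputs of the three examples above:

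| Endpoint | 15 mg | 5 mg | As written |
|---|---|---|---|
| HbA1c | 0.95 | 0.92 | same |
| FPG | 0.88 | 0.85 | same |
| Body weight | 0.81 | 0.79 | same |
| HbA1c <7.0% | 0.65 | 0.56 | 0 |
| Systolic BP | 0.26 | 0.17 | 0 |
| Diastolic BP | 0.13 | 0.10 | 0 |

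A rough bracket for HbA1c <7.0% at 15 mg multiplies the chance of reaching order 7 by the stand-alone power. It gives 0.79 × 0.73 = 0.58 at the low end. If FPG and weight are taken as near certain, it gives 0.915 × 0.82 = 0.75 at the high end.

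**The case against.** The strongest reply is that this is a design preference. The six-step China sequence is explicit, prespecified and consistent across the summary, Section 2.1 and Section 9.2.2, and it controls error within China. The omitted endpoints still get China estimates and intervals, and they are formally tested in an overall population that is 80% Chinese. The stated reason is also factually fair: power for these endpoints falls short of the 95% per dose planned for HbA1c. All of that stands, and it is why the point has minor weight. It does not make low power a reason for omission under a stop-at-first-failure rule.

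A reader might infer that the China claims are given up for nothing. That goes too far. In the scenario above, the chance that the whole sequence succeeds falls from 0.79 with six steps to 0.10 with twelve, so a formal failure somewhere becomes likely. A sponsor may dislike that record, although a failure after order 6 undoes no success at orders 1-6. The chance of a false later China claim also rises from 0 to at most 0.05 when orders 1-6 are real effects. Across the two populations together, the same null tested twice gives about 0.07 (correlation √0.8). That already applies to the HbA1c tests, so the worst case does not rise.

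A reader might also infer that registration in China is put at risk. The documents state the registration purpose but do not say that an error-controlled China claim is needed on each secondary endpoint.

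**Conclusion.** The point holds as a cheap improvement of minor weight. The logical part rests on no assumption: appended tests leave the power of orders 1-6 unchanged and keep China family-wise error within 0.05, so limited power justifies late placement only.

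The size does rest on assumptions. The chance of a confirmatory China claim on HbA1c <7.0% goes from 0 to roughly 55-75% at 15 mg and 50-60% at 5 mg. For systolic and diastolic BP it goes to only about 10-30%, so the gain lies mainly in one endpoint. These ranges depend on the placebo HbA1c level, the endpoint correlations, the power for FPG and weight, and the BP SDs, none of which the plan gives. In particular, the plan gives no SD or power for FPG or weight, so passing those steps cannot be treated as certain.

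It would be wrong to read the short sequence as a statistical error. The existing procedure is valid, and no planned conclusion is biased or contradicted.

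**What to change.** Before unblinding:

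- In the Section 9.2.2 table, number the six China rows now marked not applicable as 7-12, in the overall order. At minimum, number HbA1c <7.0% as 7 (15 mg) and 8 (5 mg).
- Delete the footnote that limits China testing to three endpoints, or extend it if only HbA1c <7.0% is added. Revise the sentence giving limited power as the reason.
- In Section 2.1 and the summary objectives, extend the China range of secondary hypotheses from 1-4 to 1-10, or to 1-6 for the minimum version. Align the summary's statistical methods text.
- Keep the stop-at-first-failure rule, with nominal p-values after the first failure.

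The cost is wording only: no extra subjects or visits, and no power lost on any existing test. The price is the possible record of a formal failure late in the China sequence and the use of the 0.05 already allotted to China. If the sponsor keeps the short sequence, it should give a reason other than power.

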9.2.3. Endpoints Related to Pharmacokinetics of Ertugliflozin

Details on the pharmacokinetic analysis may be found in the Statistical Analysis Plan. The pharmacokinetic data from this trial may be combined with data from other studies for population pharmacokinetic analysis using nonlinear mixed effects modeling. If data permit, estimates of population pharmacokinetic parameters such as CL/F as well as estimates of inter-individual and residual variability will be determined. In addition, effects of demographic or physiologic factors (eg, age, race, weight, gender, renal function) on pharmacokinetic parameters will be assessed. The results will be summarized in a separate report.

9.3. Safety Analysis

The All Subjects as Treated (ASaT) population will be used for the analysis of safety data in this trial. The ASaT population consists of all randomized subjects who received at least one dose of investigational product. Subjects will be included in the treatment group corresponding to the trial treatment they actually received for the analysis of safety data using the ASaT population. All safety analyses and summaries will be produced for the overall study population as well as for the China subpopulation.

The Medical Dictionary for Regulatory Activities (MedDRA) will be used to classify all adverse events (AEs) with respect to system organ class and preferred term. Summaries of AEs will include treatment-emergent AEs according to treatment group.

To avoid the confounding influence of rescue therapy, the primary approach for most safety analyses will exclude data from the period following the initiation of rescue therapy. A secondary approach will include data following the initiation of rescue therapy. For serious AEs and discontinuations due to AEs, the approach that includes data following the initiation of rescue therapy will be considered primary.

Descriptive statistics will be used to summarize results and changes from baseline in clinical laboratory tests and in vital signs. The number and percentage of subjects with abnormal findings from ECGs will be tabulated by treatment group.

Furthermore, a 3-tier approach will be used to summarize AEs. Tier-1 AEs consist of pre-specified adverse events and will include AEs or collections of AEs related to urinary tract infection, genital mycotic infection, symptomatic hypoglycemia and hypovolemia. Where available, standard MedDRA queries will be used to pool different AE terms that are related to the Tier-1 AEs. The precise AE terms that will contribute to the Tier-1 endpoints will be determined prior to unblinding. For these events, the percentage of subjects with incident AE, the risk difference, its 95% confidence interval, and p-value will be provided. The confidence intervals and p-values are not adjusted for multiplicity and therefore must be considered accordingly. Tier-2 AEs are those that are not Tier-1, but are common, occurring in at least 4 subjects in any treatment arm. The cut-off of at least 4 events was chosen because the 95% confidence interval for the between-group difference in percent incidence will always include zero when treatment groups of equal size each have less than 4 events and so adds little to the interpretation of potentially meaningful differences. For these events,

the percentage of subjects with incident AE, the risk difference and its 95% confidence interval will be provided. The confidence intervals are for estimation purposes only. Tier-3 AEs are all other AEs (neither Tier-1 nor Tier-2). For Tier-3 AEs, only within-group incidence proportions will be tabulated.

9.4. Data Monitoring Committee

This trial will use an external Data Monitoring Committee (E-DMC).

The E-DMC will be responsible for ongoing monitoring of the safety of subjects in the trial according to the Charter will describe the precise mandates of the E-DMC. The recommendations made by the E-DMC to alter the conduct of the trial will be forwarded to the Sponsor for final decision. The E-DMC charter will specify the role and responsibilities of the E-DMC and also the contact individuals within the Sponsor organization and the E-DMC responsible for communications between these organizations. The Sponsor will forward such decisions, which may include summaries of aggregate analyses of endpoint events and of safety data which are not endpoints, to regulatory authorities, as appropriate.

10. QUALITY CONTROL AND QUALITY ASSURANCE

During study conduct, Pfizer/Merck or their agents will conduct periodic monitoring visits to ensure that the protocol and Good Clinical Practices (GCPs) are being followed. The monitors may review source documents to confirm that the data recorded on CRFs is accurate. The Investigator and institution will allow Pfizer/Merck monitors/auditors or its agents and appropriate regulatory authorities direct access to source documents to perform this verification.

The study site may be subject to review by the Institutional Review Board (IRB)/Independent Ethics Committee (IEC), and/or to quality assurance audits performed by Pfizer, or companies working with or on behalf of Pfizer, and/or to inspection by appropriate regulatory authorities.

It is important that the Investigator(s) and their relevant personnel are available during the monitoring visits and possible audits or inspections and that sufficient time is devoted to the process.

